### **Estimation of sample size**

Our recent study showed that CAT treatment for 8 weeks produced a  $2.3 \pm 2.8$  (SD) score greater improvement than control (minimum acupuncture stimulation, MAS) on MoCA in patients with poststroke cognitive impairment. One similar trial has reported that acupuncture treatment alone for 3 months yielded a  $1.9 \pm 4.1$  greater improvement than nimodipine, a commonly used anti-hypertension drug, on MoCA in patients with poststroke cognitive impairment. Based on these two trials, we expect that CAT could yield an average  $2.1$  [ $(2.3+1.9)/2 = 2.1$ ] score greater improvement on MoCA than routine care, with an average standard deviation (SD) equal to a 1.7-fold of mean difference [ $(2.8/2.3 + 4.1/1.9)/2 = 1.7$ ], i.e.,  $SD = 1.7 \times 2.1 = 3.6$ . The following formula is then used to further calculate the sample size:

$$n = \frac{2}{(M/SD)^2} \times C_{p,\text{power}}$$

where  $n$  is the number of subjects required in each arm and  $M$  is the mean difference that is equal to 2.1.  $SD$  is the standard deviation that is 3.6.  $C_{p,\text{power}}$  is equal to 7.9 when the two-tailed level of  $\alpha$  and power ( $1-\beta$ ) are set at 0.05 and 80%, respectively. It requires 62 subjects per arm, with an assumed dropout rate of 25%. We propose to recruit a total of 248 subjects ( $n = 62$  per arm for 4 arms).

## Methods

### **Screening**

Screening will be conducted by general physicians, registered occupational therapists, social workers, and research assistants in nursing and care homes.

## **Randomization, central allocation and blindness**

One independent research assistant will be in charge of randomization and central allocation as the central coordinator. After confirmation of patients' eligibility and completion of the baseline assessment, participants will be randomly assigned to CAT, CAE, CAT+CAE, or routine care groups in a ratio of 1:1:1:1. Random codes were produced in advance using simple, complete, non-sequential numbers, with a block of 4, 8 and 12, through a random allocation software at <http://mahmoodsaghaei.tripod.com/Softwares/randalloc.html>. Randomization information will be sealed in sequentially numbered opaque envelopes.

Central allocation will be conducted, i.e., site investigators who are responsible for subjects' eligibility will obtain the opaque envelope from the central coordinator for an eligible subject who will be allocated to one of the four groups. Each envelope will be opened by acupuncturists after the participant completes the baseline assessment. Clinical assessors and data analysts will be blind to patients' treatment.

## **Treatment procedure**

(a) Routine care: All participants in the four groups will continue their current routine care and medications as usual. These routine cares will serve as covariates included in outcome analysis.

(b) CAT regimen: Subjects assigned to the CAT group will receive CAT treatment in addition to routine care. CAT will be conducted for 2 sessions per week for 12 consecutive weeks, a total of 24 treatment sessions. Registered Chinese medicine practitioners (CMPs) with a master's degree or above and with at least 5 years of acupuncture experience will be responsible for acupuncture treatment. A brief introduction to acupuncture procedures will be given by a CMP during the first visit. Details of selected acupoints are illustrated and summarized in [Figure 2](#) and [Table 1](#).

The acupuncture treatments will be conducted at the subjects' corresponding care homes. Each subject will receive a maximum of 26 needles per treatment session, adjusted by their tolerance, in a supine position. The following 14 body acupoints with only manual stimulation will be used: Shenmen (HT7, 神門), Hegu (LI4, 合谷), Waiguan (TH5, 外關), Zusani (ST36, 足三里), Fenglong (ST40, 豐隆) and Sanyinjiao (SP6, 三陰交) on both sides, and Zhongwan (CV12, 中脘) and Guanyuan (CV4, 關元) in the midline. Meanwhile, electrical stimulation will be conducted on six pairs of frontal acupoints with positive (+) and negative (-) electrode cord connections as follows: Baihui (GV20, 百會) and Yintang (EX-HN3, 印堂), left Sishencong (EX-HN1, 四神聰) and Toulinqi (GB15, 頭臨泣), right Sishencong (EX-HN1, 四神聰) and Toulinqi (GB15, 頭臨泣), bilateral Shuaigu (GB8, 率谷), bilateral Taiyang (EX-HN5, 太陽), and bilateral Touwei (ST8, 頭維).

Disposable acupuncture needles with 0.25 mm in diameter and 25 or 40 mm in length (Agent: MOCM International Medical Instrument Limited; manufacturer: Wuxi Jiajian Medical Instrument Co., Ltd.) will be inserted at a depth of 10-30 mm perpendicularly or obliquely into acupoints. Manual manipulation will be carried out on all acupoints to evoke a needling sensation *de qi*. Electrical stimulation is additionally delivered on the 6 pairs of frontal acupoints. The output peak current and voltage of the machine (model: ITO ES-360) are 6 V and 48 mA, respectively, with a constant wave at a frequency of 2 Hz and a phase duration of 100 µs for 30 minutes. The stimulation intensity will be adjusted to a level at which patients feel most comfortable. The low frequency could produce broader neuromodulation compared to the higher frequency. The electrical stimulation will be adjusted according to the patients' tolerance. Each session of treatment will last for 30 minutes.

(c) CAE regimen: Subjects assigned to the CAE group will receive CAE in addition to routine care. The detailed procedure for CAE is summarized in [Table 2](#). CAE interventions will be conducted 3 times per week for 12 consecutive weeks, a total of 36 treatment sessions. Trained research assistants or registered CMPs will be responsible for CAE treatment. CAE consists of 12 steps that take about 15 minutes to complete and mainly concentrate on the acupoints on the face, head, neck, and shoulder. All chosen acupoints are easily localized and conveniently operated by informal caregivers after proper

training. All techniques that demand professional training or involve potential risks (e.g., joint mobilization) are excluded.

(d) CAT+CAE: Subjects assigned to the CAT+CAE group will receive CAT+CAE in addition to routine care. The procedure is a combination of CAT+CAE as described above.

(e) Post-trial treatment of subjects in the routine care group: Those who are initially assigned to the routine care group will have a choice to receive CAT, CAE, or CAT+CAE treatment for 12 weeks after they complete the trial. The post-trial treatment will serve as compensation for their participation.

(f) Termination criteria and post-termination management: To ensure participants' safety, those who cannot tolerate acupuncture or acupressure or are hospitalized due to the aggravation of their condition will be discontinued from the study and given individual clinical treatment.

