### **Assessment**

(a) Primary outcome: The primary outcome will be evaluated by the mean change of the Montreal Cognitive Assessment (MoCA) score between baseline and endpoint. The MoCA test assesses seven domains of cognitive function, including visuospatial, naming, attention, language, abstraction, recall, and orientation domains, for a total possible score of 30 points. It has been well established for the detection of MCI, with sensitivity for detecting MCI of 90% compared to 18% for the Mini-Mental State Examination (MMSE), and the evaluation of the severity of cognitive impairment. A score of 25 points or less is indicative of cognitive impairment, but the score needs to be adjusted for age and education. We have applied MoCA in the two previous studies.

(b) Secondary outcomes: The secondary outcomes will include the Digit span test for attentional function, short-term memory, and working memory, the Modified Barthel Index (MBI) for functional independence, the Visual Analogue Scale (VAS) for pain, the 15-item Geriatric Depression Scale (GDS-15) for depression, and the Insomnia Severity Index (ISI) for insomnia.

Digit Span is a measure of working and short-term memory, and is evaluated in two formats, Forward Digit Span and Reverse Digit Span, with a total possible score of 14 points, respectively. The Digit span test is a simple test to further evaluate subjects' attentional function, short-term memory, and working memory.

MBI is a validated outcome measure to evaluate the functional status of patients. MBI consists of 10 items, i.e., feeding, bathing, grooming, dressing, bowel control, bladder control, toileting, chair transfer, ambulation, and stair climbing, to score with a five-step scoring system. MBI score ranges from 10 to 50, with a higher score indicating a higher level of independence. VAS is a simple instrument to measure subjective experience in pain. A horizontal line that represents the severity of symptoms from 0, no pain, to 10, very severe pain, is shown, and the patient should mark the point on the line that reflects the subject's perception of the current state. Functional independence and pain are measured, as previous studies have confirmed the benefits of acupressure and acupuncture in improving disability and pain.

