### **Data processing and analysis**

One biostatistician who is blinded to interventions will be responsible for statistical analysis. The analysis will be carried out on the intention-to-treat (ITT) population, for which participants have been randomized. A linear mixed-effect model will be applied to compare the primary outcome (changes in total MoCA score from baseline) and secondary outcomes (changes in scores of the Digit span test, MBI, VAS, GDS and ISI), with time (baseline, week 6, and week 12) and group (CAT, CAE, CAT+CAE, and routine care) as categorical fixed factors and random intercepts within a scaled identity covariance matrix. Gender, age, baseline MoCA score, and baseline medication will serve as covariates. Subgroup analysis will be further conducted to compare outcomes by gender, age, and severity of dementia to detect whether these factors are associated with the outcomes. Pairwise comparisons will be further carried out to examine between-group differences. One-way analysis of variance (one-way ANOVA) will be used to detect differences in continuous baseline variables. Categorical baseline variables, including discontinuation and incidence of AEs, will be analyzed using the Chi-square test or Fisher's exact test. Statistical significance was defined as a two-tailed  $P < 0.05$ . The analysis will be conducted using R Studio software.

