### **Termination criteria**

(a) Premature termination or suspension of study: The study will be completed as planned unless one or more of the following criteria are satisfied that require temporary suspension or early termination of the study: (1) new information or other evaluation regarding the safety or efficacy of the study drug that indicates a change in the known risk/benefit profile for the compound, such that the risk/benefit is no longer acceptable for subjects participating in the study; (2) a significant violation of Good Clinical Practice (GCP) that compromises the ability to achieve the primary study objectives or compromises subject safety.

(b) Premature termination or suspension of investigational sites: A study site may be terminated prematurely or suspended if the site (including the investigator) is found to be in significant violation of GCP, protocol, or contractual agreement, is unable to ensure adequate performance of the study, or

is otherwise permitted by the contractual agreement.

(c) Procedures for premature termination or suspension: In the event that the PI, an institutional review board (IRB) / research ethics committee (REC) or a regulatory authority elects to terminate or suspend the study or the participation of an investigational site, a study-specific procedure for early termination or suspension will be provided by the PI; the procedure will be followed by applicable investigational sites during the course of termination or study suspension.

(d) Criteria for discontinuation or withdrawal of a subject: (1) pretreatment event or AE: the subject has experienced a pretreatment event or AE that requires early termination because continued participation imposes an unacceptable risk to the subject's health or the subject is unwilling to continue because of the pretreatment event or AE; (2) major protocol deviation: the discovery post-randomization that the subject failed to meet protocol entry criteria or did not adhere to protocol requirements, and continued participation poses an unacceptable risk to the subject's health; (3) lost to follow-up: the subject does not return to the site, and attempts to contact the subject are unsuccessful; (4) withdrawal of consent: the subject wishes to withdraw from the study; (5) study termination: the PI, IRB, REC, or regulatory agency terminates the study.

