(e) Procedures for discontinuation or withdrawal of a subject: The investigator may terminate a subject's study participation at any time during the study when the subject meets the study termination criteria. In addition, a subject may discontinue his or her participation without giving a reason at any time during the study. Should a subject's participation be discontinued, the primary criterion for termination would be recorded. Subjects who discontinue the study during the treatment period will visit the site as soon as possible for clinical assessment, if applicable. To ensure participants' safety, those discontinued because of severe side effects or hospitalizations due to any reason will be given individual clinical treatment. Discontinued or withdrawn subjects will not be replaced.

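### Participants who cannot tolerate treatment or are hospitalized for aggravation leave follow-up, and no analysis tests the missing-at-random assumption on which their Week-12 MoCA then depends

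*Protocol*

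**What the plan says.** Protocol, Treatment procedure (f), states that "those who cannot tolerate acupuncture or acupressure or are hospitalized due to the aggravation of their condition will be discontinued from the study". The Assessment section and Table 3 schedule MoCA at baseline, week 6 and week 12 only, and nothing continues that schedule after discontinuation. Under Termination criteria (e), "Subjects who discontinue the study during the treatment period will visit the site as soon as possible for clinical assessment, if applicable". That sentence does not name MoCA, and the SAP does not say how such a visit would be used.

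On the analysis set, the protocol says: "The analysis will be carried out on the intention-to-treat (ITT) population, for which participants have been randomized". The SAP adds completion of the baseline assessment and sets compliance aside. Its Missing data section specifies a mixed model fitted to the available data with nothing imputed; the time levels are baseline, week 6 and week 12. Beyond that model the plan has only pairwise comparisons and subgroups. Neither document names a sensitivity analysis for missing data.

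The protocol's Assessment section states: "The primary outcome will be evaluated by the mean change of the Montreal Cognitive Assessment (MoCA) score between baseline and endpoint". No week is given; I read the endpoint as Week 12.

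The plan has relevant safeguards:
- "Each subject will receive a maximum of 26 needles per treatment session, adjusted by their tolerance, in a supine position", and electrical stimulation is likewise adjusted to tolerance.
- On discontinuation, "the primary criterion for termination would be recorded".
- The SAP plans a CONSORT diagram and a comparison of discontinuation across the four groups.

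**The concern.** The analysis set follows the intention-to-treat principle, but data collection does not. Someone who stops treatment stays in the set, yet the rule stops the scheduled outcome being collected. The reasons for leaving, intolerance or aggravation, may be related to the outcome.

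Loss may also differ by arm. Intolerance of treatment can arise only in the three active arms, while hospitalization can occur in all four. Active-arm participants are asked about adverse events at every session, routine-care participants only at baseline, week 6 and week 12. Routine-care participants are offered active treatment after completing the trial, which may help retention in that arm.

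The safeguards can reduce an imbalance or make it visible. They cannot show whether the estimated effect survives it. A reader would learn that loss differed by arm, but not whether a positive or null MoCA result would hold under another plausible assumption about those who left.

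**Working it through.** **Inputs from the plan** (sample-size sections of both documents): difference 2.1, SD 3.6, multiplier 7.9, two-sided 5%, power 80%, dropout 25%, 62 per arm.

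**1. Reproduce the plan's figure.** n = 2/(2.1/3.6)² × 7.9 = 46.43, and 46.43/0.75 = 61.9, so 62 per arm. The plan thus allows for losing 0.25 × 62 = 15.5 people per arm.

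**2. Simple bias formula.** Let f be the share missing Week 12 and d the leavers' shortfall below the model's prediction given their observed data. Then bias = fA × dA − fC × dC (A active, C routine care). Both f and d are my assumptions; d is set at 2.1, the plan's own difference. The 25% is all-cause dropout, so it is an upper case for exits under rule (f); 5% and 10% stand for those exits being only part of it.

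| Missing, active vs routine care | Bias (MoCA points) |
|---|---|
| 5% vs 0% | 0.05 × 2.1 = +0.11 |
| 10% vs 0% | 0.10 × 2.1 = +0.21 |
| 25% vs 10% | 0.525 − 0.21 = +0.32 |
| 25% vs 0% | 0.25 × 2.1 = +0.53 |
| 25% vs 25% | 0 |
| 10% vs 25% | 0.21 − 0.525 = −0.32 |

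**3. How much the Week-6 score recovers.** Suppose active-arm leavers are 1.05 points below stayers at Week 6 and 2.1 below at Week 12. A random-intercept model was fitted in large samples to change rows at baseline (all zero), week 6 and week 12. It included group by visit, because SAP Table 2 reports the weeks separately, and left out covariates. Bias by Week-6/Week-12 correlation:

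| Missing | 0.3 | 0.5 | 0.7 |
|---|---|---|---|
| 25% vs 0% | 0.492 | 0.475 | 0.460 |
| 10% vs 0% | 0.197 | 0.189 | 0.183 |
| 5% vs 0% | 0.098 | 0.095 | 0.092 |

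Equal loss of 25% gives 0. A simulation at 62 per arm with 16 vs 0 missing gave 0.51, 0.54 and 0.43 (simulation standard error about 0.04), consistent with the first row.

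Hand check at correlation 0.5: the zero baseline row roughly halves the correlation the model works with, to 0.25. The weight on the Week-6 score is then 0.25/1.25 = 0.20, and the bias is about 0.25 × (2.1 − 0.20 × 1.05) = 0.47.

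If only post-baseline rows are modelled, the weight is the correlation itself: 0.25 × (2.1 − 0.5 × 1.05) = 0.39. Across the three correlations this gives 0.45, 0.39 and 0.34. The SAP names three time levels, so the table is the literal reading.

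**4. Scale.** Completers per arm: 62 × 0.75 = 46.5. SE = 3.6 × √(2/46.5) = 0.747. Smallest significant difference: 1.96 × 0.747 = 1.46.

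**5. Tipping point.** Take 25% missing in both arms, with a shift delta in the active arm only. Delta = −2.1 lowers the estimate by 0.525, so observed differences from 1.46 up to 1.463 + 0.525 = 1.99 lose significance. An observed 2.1 does so at a downward shift of (2.1 − 1.463)/0.25, about 2.5 points. This ignores covariates, Week-6 information and any change in SE.

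**The case against.** The early visit may be worth more than it first appears. The protocol uses the term clinical assessment for the scheduled battery in Table 3, which includes MoCA, so an exit MoCA is a natural reading. The endpoint week is not named, so an exit score is not expressly excluded. This stands to the extent that some post-discontinuation scores may exist. But the visit is conditional, is not a Week-12 measurement, and has no stated place in a model with three fixed time levels.

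The magnitudes are assumed. No arm-specific loss, split of reasons or leaver deficit is documented; 25% against none is extreme, and the tipping-point figures put the shift in one arm only. This stands. At 5% to 10% the bias is roughly 0.1 to 0.2 points against a smallest significant difference of 1.46, and it shrinks or reverses if routine-care leavers also do worse than predicted.

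Three smaller points also stand. No passage shows how often a MoCA is feasible after intolerance or hospitalization. The value 2.1 has a natural meaning in active arms (all benefit lost) but is only a convention in routine care. Wording differences elsewhere, for example "those discontinued because of severe side effects or hospitalizations due to any reason will be given individual clinical treatment" under Termination criteria (e), concern care after exit and do not clearly contradict rule (f); nothing here rests on them.

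Finally, a mixed model without imputation is an acceptable primary method, and the exit reasons, CONSORT diagram and discontinuation test are real safeguards. None of them checks robustness of the effect estimate.

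**Conclusion.** The concern holds. A stated rule gives up scheduled outcome data that the intention-to-treat set calls for, and nothing in the plan tests the assumption that replaces those data. No error in the mixed model or the sample size is claimed, and no view is taken on when treatment should stop.

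The illustrated bias runs from −0.32 to +0.53 MoCA points depending on how loss and deficit fall across arms. It is about 0.1 to 0.2 when 5% to 10% are lost from the active arm alone. A small bias would matter mainly for a result near the 1.46 threshold; a planned-size difference of 2.1 would need about 25% missing and a shift near 2.5 points in the active arm only. The actual rates are unknown, which is the reason to plan the check in advance. It is a change the plan should make; without it the primary analysis still stands, but its robustness goes unexamined.

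**What to change.** 1. **Protocol, one sentence.** State that stopping treatment does not by itself end follow-up: consenting participants are assessed at the scheduled Week-6 and Week-12 visits where feasible, and those values enter the intention-to-treat model. The treatment-stopping rule stays as it is.
2. **SAP, one paragraph.** Pre-specify a delta-adjusted (tipping-point) analysis of missing Week-12 MoCA. Vary delta separately in the active and routine-care arms from 0 to −2.1 points, then further until the conclusion changes.

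Supporting text: name Week 12 as the endpoint if that is intended; say how the early visit is used; add missing Week-12 MoCA by arm and reason to the planned discontinuation summary. While editing, reconcile the scope wording of Treatment procedure (f) with Termination criteria (d) and (e); I take no position on which is right.

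The cost is that text plus a few extra assessments by assessors already deployed to the sites. Some hospitalized participants will not be assessable, and those who withdraw consent or are lost to follow-up will not be recovered. The estimated effect may become less favourable.

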### **Control group**

The group that receives routine care only will serve as the control group. For acupuncture, sham acupuncture techniques such as Streitberger needle may not be suitable for elderly subjects as they are associated with an increased risk of skin injury. Also, sham acupuncture has been proved not to be an inert method. For acupressure, the CAE regimen involved multiple steps like pressing and kneading different body parts. Typical sham acupressure procedures, like using a non-acupoint or placebo acupressure device, are not applicable for the CAE treatment.

### **Assessment**

(a) Primary outcome: The primary outcome will be evaluated by the mean change of the Montreal Cognitive Assessment (MoCA) score between baseline and endpoint. The MoCA test assesses seven domains of cognitive function, including visuospatial, naming, attention, language, abstraction, recall, and orientation domains, for a total possible score of 30 points. It has been well established for the detection of MCI, with sensitivity for detecting MCI of 90% compared to 18% for the Mini-Mental State Examination (MMSE), and the evaluation of the severity of cognitive impairment. A score of 25 points or less is indicative of cognitive impairment, but the score needs to be adjusted for age and education. We have applied MoCA in the two previous studies.

(b) Secondary outcomes: The secondary outcomes will include the Digit span test for attentional function, short-term memory, and working memory, the Modified Barthel Index (MBI) for functional independence, the Visual Analogue Scale (VAS) for pain, the 15-item Geriatric Depression Scale (GDS-15) for depression, and the Insomnia Severity Index (ISI) for insomnia.

Digit Span is a measure of working and short-term memory, and is evaluated in two formats, Forward Digit Span and Reverse Digit Span, with a total possible score of 14 points, respectively. The Digit span test is a simple test to further evaluate subjects' attentional function, short-term memory, and working memory.

MBI is a validated outcome measure to evaluate the functional status of patients. MBI consists of 10 items, i.e., feeding, bathing, grooming, dressing, bowel control, bladder control, toileting, chair transfer, ambulation, and stair climbing, to score with a five-step scoring system. MBI score ranges from 10 to 50, with a higher score indicating a higher level of independence. VAS is a simple instrument to measure subjective experience in pain. A horizontal line that represents the severity of symptoms from 0, no pain, to 10, very severe pain, is shown, and the patient should mark the point on the line that reflects the subject's perception of the current state. Functional independence and pain are measured, as previous studies have confirmed the benefits of acupressure and acupuncture in improving disability and pain.

The GDS-15 consists of 15 questions in which subjects are asked to respond by answering yes or no in reference to how they felt over the past week. Of the 15 items, 5 items (question numbers 1, 5, 7, 11, 13) indicate depression when answered negatively, while the rest (question numbers 2, 3, 4, 6, 8, 9, 10, 12, 14, 15) indicate the presence of depression when answered positively. The GDS-15 score is interpreted as follows: normal (0-4), mild depression (5-8), moderate depression (9-11), and severe depression (12-15). GDS can be used in mild to moderately cognitively impaired older adults. ISI is a

validated 7-item scale to assess the severity of insomnia. The total score ranges from 0 to 28, with scores of 0-7 indicating no clinically significant insomnia, 8-14 indicating subthreshold insomnia, 15-21 indicating moderate insomnia, and 22-28 indicating severe insomnia. Depressive and sleep symptoms are investigated because elderly people with cognitive impairment often have comorbid emotional and sleep disorders. The benefits of acupuncture and acupressure for depression and insomnia have been confirmed in our previous studies.

(c) Adverse events: The severity of adverse events (AEs) will be assessed according to the Common Terminology Criteria for Adverse Events (CTCAE) v5.0 criteria. AEs will be systematically recorded, in which AEs that first appear in the study or worsen relative to the pre-study status will be recorded at each visit, including the date and time of onset, duration, severity, relationship to intervention, and action taken accordingly. All possible events will be independently evaluated by staff who do not assess treatment outcomes. The causality between treatment procedures and AEs will be assessed.

Fatal or life-threatening unexpected AEs will be reported to the regulatory bodies as soon as possible but no later than 7 calendar days after first knowledge by the principal investigator (PI) that a case qualifies, followed by as complete a report as possible within 8 additional calendar days. This report would include an assessment of the importance and implications of the findings, including relevant previous experience with the same or similar medicinal products. For other serious, unexpected AEs that are not fatal or life-threatening, they will be reported as soon as possible but no later than 15 calendar days after first knowledge by the PI or that the case meets the minimum criteria for expedited reporting. For non-serious AEs and serious AEs that are expected, they will be reported in a brief summary at the conclusion of the trial.

(d) Assessment schedule: Clinical assessment will be conducted at baseline, week 6, and week 12 (Table 3). For AEs, participants in active treatment groups will be asked whether they have experienced any AEs on each treatment and assessment session. Participants in the control group will be recorded for all AEs on a regular basis (baseline, 6, and 12 weeks).

